7.3.1 General statistical issues

This design has acceptable properties in terms of the false positive potential, controlling the overall type I error at 9.7%, for each of the two treatment comparisons.

Sobi	
Emapalumab/Anakinra	Clinical Study

Secondary endpoints will be evaluated in a descriptive way. In some cases p-value comparisons will be undertaken, but these are to be interpreted in an exploratory way.

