Prophylactic Therapy: For patients randomized to emapalumab, prophylaxis for Herpes Zoster virus infection has to be in place from the day before initiation of emapalumab treatment until end of study Concomitant Therapy: Concomitant use of IL-6 inhibitors (e.g., tocilizumab), non-anakinra IL-1 inhibitors (e.g, canakinumab), TNF inhibitors and JAK inhibitors is not allowed. If any of these therapies are initiated at the discretion of the Investigator e.g., as rescue therapy due to worsening of the patient's condition, then the patient should be withdrawn from study. Hydroxychloroquine, chloroquine, glucocorticoid treatment, antimicrobial therapy and prophylaxis are not limited. Analgesic treatment, transfusion of blood products, electrolyte and glucose infusions, i.v. parenteral nutrition, positive inotropic support, antibiotics, antifungal and anti-viral treatments (e.g., remdesivir), ultrafiltration or hemodialysis, as well as general supportive care are permitted. The study will enroll a total of 54 patients, 18 per arm according to the 1:1:1 Determination of sample randomization. Patients will be stratified based on glucocorticoid treatment at size: randomization to ensure an equal distribution between treatment arms. The sample size has been estimated based on the following assumptions: An overall one-sided significance level for efficacy of 0.097 (9.7%) 1. and a power of 74% for each comparison under the assumption that the true success rates are 50% in the SoC group increasing to 80% in the emapalumab or anakinra groups. 2. The study will consist of two stages, with equal numbers of patients randomised into Stage 1 and into Stage 2 per treatment arm. 3. There is the potential to stop for futility of emapalumab or anakinra (or both) at the end of Stage 1. 4. The futility rule for stopping at the end of Stage 1 is binding.

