7.1 Determination of sample size

The study will enroll a total of 54 patients, 18 per arm according to the 1:1:1 randomization.

The sample size has been estimated based on the following assumptions:

- An overall one-sided significance level for efficacy of 0.097 (9.7%) and a power of 74% for each comparison under the assumption that the true success rates are 50% in the SoC group increasing to 80% in the emapalumab or anakinra groups.
- The study will consist of two stages, with equal numbers of patients randomised into Stage 1 and into Stage 2 per treatment arm.
- There is the potential to stop for futility or for efficacy of emapalumab or anakinra (or both) at the end of Stage 1, but only the futility rule is binding and irrespective of the Stage 1 results, the study will not be stopped for efficacy but continue to accrue safety data.

More specifically:

• The emapalumab or anakinra arm (or both) will be stopped at the end of Stage 1 for futility if the one-sided p-value in favour of emapalumab/anakinra is > 0.690.

Confidential

- Efficacy of the emapalumab or anakinra arm (or both) will be declared at the end of Stage 1 if the one-sided p-value in favour of emapalumab/anakinra is < 0.025.
- If the trial continues to Stage 2, efficacy will be declared at the end of Stage 2 if the onesided p-value in favour of emapalumab/anakinra is < 0.159.

The calculations on the operating characteristics of this design have been undertaken using PASS, Version 14: Group-Sequential Tests for Two Proportions (Simulation).

The value for the type I error has been chosen in recognition of the urgent unmet medical need to allow the identification of a signal, at least, from a statistical perspective. Having seen a statistical signal, it is then a matter of evaluating whether the observed treatment differences represent clinically relevant effects that can satisfy that unmet need.

Assuming no untoward safety signal is observed and no futility stopping occurs at the Stage 1 interim, the decision may be taken to increase the sample size beyond 54 patients in order to accrue further safety and efficacy data. Details of this would be described in a protocol amendment.

In case the outcome is statistically convincing, i.e. statistically significant on a 5% level in the stage 2 analysis, efficacy will be considered confirmed and the results may, where warranted, be used to seek regulatory approvals.

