7.3.6 Interim analysis

The study will consist of one interim analysis (Stage 1) and a final analysis (Stage 2), with approximately the same numbers of patients randomised into Stage 1 and into Stage 2 per treatment arm. The Stage 1 interim analysis will be conducted after the accrual of at least 9 patients per treatment arm. See Section 7.1 for further details concerning the interim analysis.

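### The planned two-stage design has a one-sided type I error of 11.7% per comparison at the assumed 50% control rate, not the stated 9.7%

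*Protocol*

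**What the plan says.** Protocol 7.1 gives "An overall one-sided significance level for efficacy of 0.097 (9.7%) and a power of 74% for each comparison", on the assumption that the "true success rates are 50% in the SoC group increasing to 80% in the emapalumab or anakinra groups". SAP 6 and the protocol synopsis repeat the 9.7% and the 74%. Protocol 7.3.1 goes further than reporting a design value: it says the design has acceptable false-positive properties, "controlling the overall type I error at 9.7%, for each of the two treatment comparisons".

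The decision rule is set out in these places:

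- **Size:** "The study will enroll a total of 54 patients, 18 per arm according to the 1:1:1 randomization" (Protocol 7.1).
- **Stages:** "The study will consist of two stages, with equal numbers of patients randomised into Stage 1 and into Stage 2 per treatment arm" (Protocol 7.1). Protocol 7.3.6 adds: "The Stage 1 interim analysis will be conducted after the accrual of at least 9 patients per treatment arm".
- **Stage 1:** an arm stops "for futility if the one-sided p-value in favour of emapalumab/anakinra is > 0.690", and this rule is binding. Efficacy is declared if p < 0.025 (Protocol 7.1).
- **Stage 2:** efficacy is declared if p < 0.159 (Protocol 7.1). SAP Table 1 lists outcomes out of 18 per arm, so the Stage 2 test uses cumulative data.
- **Test:** Fisher's exact test for each active arm against standard of care at both stages (Protocol 7.3.3.1.1, SAP 12.1), one-sided.

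The calculations are attributed to a PASS 14 simulation. Neither the number of simulated trials nor the null success rate behind 9.7% is given.

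**The concern.** The type I error follows from the rule by direct calculation, so it can be checked. The plan uses it as a justification: Protocol 7.1 and SAP 6 present the level as a deliberate choice made so that a signal can be identified, and Protocol 7.3.1 rests its claim of acceptable false-positive properties on it. If the planned design does not hold 9.7%, the trial would report a false-positive risk that is too low at the control rate the sponsor itself assumes. Anyone who recalculates the design will find the discrepancy.

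**Working it through.** **Inputs.** Stage 1 has 9 against 9 patients and Stage 2 has 18 against 18 cumulative. Success rates are 50% and 80% for power, and 50% in both arms for the null. The cut-offs are 0.025, 0.690 and 0.159.

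**Method.** For t successes on active treatment and c on control with n per arm, the one-sided Fisher p-value is p(t, c) = P(X ≥ t), where X is hypergeometric: n drawn from 2n patients of whom t + c are successes. Every Stage 1 pair (t₁, c₁) is weighted by its two binomial probabilities and classed as follows:

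- p₁ < 0.025: efficacy
- p₁ > 0.690: stop for futility
- otherwise: continue, add 9 patients per arm, and declare efficacy if p₂ < 0.159

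P(declare efficacy) = P(p₁ < 0.025) + P(0.025 ≤ p₁ ≤ 0.690 and p₂ < 0.159).

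**Step 1: reproduce the plan's own figures.** At 80% against 50%, Stage 1 efficacy is 0.1533, futility 0.1059 and Stage 2 efficacy 0.5825. Power is 0.1533 + 0.5825 = 0.7357 after rounding, against the stated 74%. The efficacy cells in SAP Table 1 also match these Fisher cut-offs at both stages. The design has therefore been read as intended.

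**Step 2: type I error.** At 50% in both arms, Stage 1 efficacy is 0.0105, futility 0.4716 and Stage 2 efficacy 0.1068. The total is 0.0105 + 0.1068 = **0.1173**, against the stated 0.097. The ratio is 0.1173 / 0.097 = 1.21. A simulation of 2,000,000 trials gave 0.1174 for type I error and 0.7358 for power.

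**Step 3: is 9.7% controlled at other success rates?**

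| Common success rate | Type I error |
|---|---|
| 50% | 11.7% |
| 45% or 55% | 11.6% |
| 40% or 60% | 11.1% |
| 35% or 65% | 10.4% |
| 31% or 69% | 9.7% |
| 30% or 70% | 9.5% |
| 20% or 80% | 7.0% |

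The maximum over a grid from 1% to 99% is 0.1173, at about 50%.

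**Step 4: other readings of the rule, at 50%.**

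| Variant | Type I error |
|---|---|
| Futility treated as non-binding | 12.4% |
| No efficacy claim at Stage 1 | 11.5% |
| Stage 1 at 10 to 12 per arm | 12.0% to 12.2% |
| Futility cells of SAP Table 1 taken literally | 12.3% (power 76.1%) |
| Mid-p | 12.8% |
| Continuity-corrected z | 12.2% |
| Pooled z | 20.3% |
| Unpooled z | 20.9% |
| Stage 2 patients tested alone | 4.0% (power 48%) |

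None gives 9.7%, and the only one below it loses the stated power.

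**Step 5: simulation noise.** With 1,000 simulated trials the standard error is √(0.1173 × 0.8827 / 1000) = 0.0102, so 0.097 is 2.0 standard errors low. With 10,000 trials it is 6.3 standard errors low.

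**Step 6: where the excess comes from.** Three Stage 2 outcomes that SAP Table 1 lists as efficacy lie just under 0.159: 11 against 7 (p = 0.1588), and 12 against 8 and 10 against 6 (both p = 0.1573).

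| Stage 2 cut-off | Maximum type I error | At 50% | Power |
|---|---|---|---|
| 0.159 | 11.7% | 11.7% | 73.6% |
| 0.158 (drops 11 v 7) | 10.5% | 10.4% | 73.2% |
| 0.155 to 0.157 (drops all three) | 9.5% | 8.3% | 71.9% |

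**The case against.** The strongest counter-argument is that 11.7% belongs to exactly balanced arms of 18 and that the trial may not end there. Stage 1 is at least 9 per arm. The mITT population drops untreated and PCR-negative patients and allows further recruitment (Protocol 7.2, SAP 7.1), and the total may be raised above 54 by amendment. Because the test is discrete, small changes matter. With Stage 1 at 9 per arm and the other rules unchanged, the maximum type I error is 8.9% for 18 against 17, 9.4% for 19 against 18, 9.6% for 18 against 16, 9.5% for 19 per arm and 8.6% for 20 per arm. These figures are correct, and they mean that the rate actually realised could fall below 9.7%. They do not rescue the statement, because the plan attaches 9.7% to 18 per arm. Equal arms of 17 or 16 also exceed it, at 11.2% and 10.6%.

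The 9.7% could also come from a null rate near 31% or 69%. The documents state neither, the only control rate they give is 50%, and a figure exceeded everywhere between those two rates is not controlled.

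On importance, the excess is 2 percentage points in a study described as proof of concept with an openly lenient level. The three cut-offs are unambiguous as thresholds. The separate 5% criterion at Stage 2 for regarding efficacy as confirmed does not use 9.7%. All of that stands and limits the consequence, but the figure is still wrong.

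**Conclusion.** The concern holds. Under the stated rule with 9 and then 18 evaluable patients per arm, the one-sided type I error per comparison is 11.7% at the assumed 50% control rate, and that is its maximum. The 9.7% is about 2 percentage points too low, and the claim of control fails for any common success rate between about 31% and 69%. The result rests on balanced arms of the planned size, cumulative data at Stage 2 and the p > 0.690 futility text. The power calculation on the same basis agrees with the plan, which supports that reading. If the futility cells in SAP Table 1 apply instead, the figure is 12.3%.

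This is a per-comparison result. The plan openly makes no adjustment across the two arms, and the chance of at least one false positive (about 19% at 50%) is a separate matter.

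**What to change.** Replace 0.097 (9.7%) with 0.117 (11.7%) in the synopsis, Protocol 7.1, Protocol 7.3.1 and SAP 6. State with it that this is the maximum over common success rates, reached at 50%, for 9 and then 18 evaluable patients per arm. In Protocol 7.3.1, tie the word for control to that figure. Add that the value will be recalculated for the evaluable numbers actually obtained. Reconcile the futility cells in SAP Table 1 with the p > 0.690 text: by Fisher's test, ties such as 7 against 7 (p = 0.712) already exceed 0.690, while the table starts with standard of care ahead by two or more. The figure depends on which applies. The cost is wording only, with no extra patients and no change to the efficacy cut-offs.

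If 9.7% must be kept, change the Stage 2 cut-off to p < 0.155, before any Stage 1 data are seen. The maximum type I error is then 9.5%. This is a design change:

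- stated power falls from 74% to 72%
- the rows 12 v 8, 11 v 7 and 10 v 6 in SAP Table 1 no longer qualify as Stage 2 efficacy and must be revised
- the Stage 2 confidence coefficient of 84% becomes 1 − 0.155 = 84.5%

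It needs no extra patients.

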7.3.2 Demographics and baseline characteristics

Demographic and baseline characteristics will be summarized in appropriate tabular presentations.

For measurements of continuous endpoints, summary statistics will include n, mean, median, standard deviation, minimum and maximum values. For categorical variables, summary tabulations of the number and percentage within each category (with a category for missing data) of the parameter will be presented.

7.3.3 Analysis related to primary objective

7.3.3.1 Primary endpoint

7.3.3.1.1 Treatment success

For the analysis of the primary endpoint, each of the pairwise comparisons, emapalumab/anakinra versus standard of care, at both the end of Stage 1 and at the end of Stage 2, will be undertaken using Fishers Exact test comparing the proportion of patients with treatment success. This will be supplemented by the presentation of one-sided exact confidence intervals of the differences in proportion between emapalumab/anakinra and standard of care, with confidence coefficients of 97.5% at the end of Stage 1 and 84% at the end of Stage 2. Twosided confidence intervals of the proportions in each group will also be presented, using the method of Clopper-Pearson [18].

The primary analysis will not adjust for the stratification factor glucocorticoid use at inclusion due to the small sample size at Stage 1. However, a sensitivity analysis of the primary endpoint using exact logistic regression will be performed at Stage 1 and 2. This will allow for conditional testing of the treatment effect given the stratification factor. The results of the analysis will be presented in terms of model-adjusted treatment success rates for each treatment group, and p-values and confidence intervals for the odds ratio of the pairwise comparisons to the standard-of-care arm.

7.3.3.2 Secondary endpoints supporting the primary objective

7.3.3.2.1 Time to mechanical ventilation and overall survival

Analysis of the time to mechanical ventilation from the point of randomization will be undertaken by plotting Kaplan-Meier curves for each of the 3 treatment groups and by pairwise comparisons (emapalumab/anakinra versus standard of care) using the logrank test. Hazard ratios will be estimated using the Cox proportional hazards model and these will be presented together with 90% two-sided confidence intervals. Overall survival (time to death from the point of randomization) and time to hospital discharge (from the point of randomization) will not be analysed at the end of Stage 2, but at the end of the follow-up period. This endpoint will be analysed as for time to mechanical ventilation.

7.3.3.2.2 Change from baseline in MEWs score

Change from baseline in MEWs score at Day 15 will be analysed using analysis of covariance (ANCOVA) including treatment arm as a fixed factor and baseline MEWs score as a covariate. Least square mean change per group, associated 90% two-sided CI, and p-values for the comparison vs. standard of care, will be presented.

7.3.3.2.3 Change from baseline in hyperinflammatory parameters

Change from baseline during treatment until Day 15 with measurements performed every 3 days of the following parameters will be summarized using descriptive statistics:

- Ferritin
- LDH
- D-dimers

7.3.3.2.4 Change from baseline in other relevant laboratory parameters

Change from baseline during treatment until Day 15 with measurements performed every 3 days of the following parameters will be summarized using descriptive statistics:

- WBC with differential counts
- RBC
- Hb
- Platelet count
- Fibrinogen
- Complement C3/C4
- Prothrombin Time
- Cardiac troponin
- Liver tests (AST, ALT, total bilirubin levels)
- CRP
- Creatinine
- Electrolytes (Sodium, Potassium, Calcium)
- Glucose

7.3.3.2.5 Change from baseline in resting SpO₂ and oxygen supplementation

Change from baseline during treatment until Day 15 with measurements performed every 3 days will be summarized using descriptive statistics for each of these parameters.

7.3.3.2.6 Change from baseline in PaO₂/FiO₂

Change from baseline (screening) during treatment until Day 15 will be summarized using descriptive statistics.

7.3.3.2.7 Change from baseline in hemogasanalysis

Change from baseline during treatment until Day 15 with measurements performed every 3 days will be summarized using descriptive statistics for each of the collected parameters.

7.3.4 Analysis related to secondary objective

7.3.4.1 Adverse events

Reported AEs during the study will be coded using MedDRA. The incidence of AEs will be summarized in frequency tables by treatment, system organ class, preferred term and maximum severity. Separate tabulations will performed for serious and non-serious AEs.

7.3.4.2 Anti-drug antibodies

The number and percentage of patients with ADA and NAb at baseline and at each post-baseline assessment will be summarized.

7.3.5 Analysis related to the exploratory objective

Clinical status using the 7-point ordinal scale is an exploratory endpoint and the data collected will be summarized to show the number and percentage of patients in each category over time.

PK and PD data will be listed and summarized at each visit with descriptive statistics.

7.3.6 Interim analysis

The study will consist of one interim analysis (Stage 1) and a final analysis (Stage 2), with approximately the same numbers of patients randomised into Stage 1 and into Stage 2 per treatment arm. The Stage 1 interim analysis will be conducted after the accrual of at least 9 patients per treatment arm. See Section 7.1 for further details concerning the interim analysis.

7.3.7 Multiple comparison/multiplicity

There will be no adjustments for multiplicity for the two pairwise treatment comparisons for the primary endpoint. Multiplicity for the sequential comparisons at the end of Stage 1 and at the end of Stage 2 are however accounted for by the design.

7.3.8 Handling of missing data

There will be no imputation of missing data for the primary endpoint (treatment success by Day 15), but patients who discontinue study treatment (or discontinue the study if randomized to standard of care) prior to Day 15 and had IMV or ECMO on their last assessment by the time of study treatment discontinuation, will be considered not having achieved treatment success by Day 15. Patients discontinuing prior to Day 15 without ever having initiated IMV/ECMO, will be considered having achieved treatment success by Day 15. Patients discontinuing prior to Day 15 will be considered having achieved treatment success. Patients who died by Day 15, have not achieved treatment success regardless of IMV/ECMO use by Day 15.

For change-from-baseline efficacy endpoints at Day 15, the last observation carried forward (LOCF) approach will be used to impute missing data, using the last post-baseline observation available for each patient.

8 Data collection, handling and record keeping

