## 8.2 Handling of missing data and outliers

### 8.2.1 Imputation of efficacy endpoints

For the primary endpoint (treatment success by Day 15), patients who discontinue study treatment (or discontinue the study if randomized to standard of care) prior to Day 15 and had IMV or ECMO on their last assessment by the time of study treatment discontinuation, will be considered not having achieved treatment success by Day 15. Patients discontinuing prior to Day 15 without ever having initiated IMV/ECMO, will be considered having achieved treatment success by Day 15. Patients discontinuing prior to Day 15 due to having significantly improved will be considered having achieved treatment success. Patients who died by Day 15, have not achieved treatment success regardless of IMV/ECMO use by Day 15.

For statistical analyses of change-from-baseline efficacy endpoints at Day 15, the last observation carried forward (LOCF) approach will be used to impute missing data, using the last post-baseline observation available for each patient.

For other efficacy presentations no imputation will be performed, i.e., all presentations will be based on observed data.

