### **8.5 Derived and computed variables**

#### **8.5.1 Treatment success**

Treatment success is achieved for patients not requiring IMV or ECMO by Day 15. If IMV or ECMO is required at any visits prior to Day 15/date of early discontinuation, but no longer required at Day 15/date of early discontinuation, treatment success has been achieved. If IMV or ECMO is not initiated during the study, treatment success has been achieved. As stated in Section 8.2.1, patients who discontinue study treatment (or discontinue the study if randomized to standard of care) prior to Day 15 and had ECMO or IMV on their last assessment by the time of study treatment discontinuation, will be considered not having achieved treatment success by Day 15. Patients who discontinue prior to Day 15 without ever having initiated IMV/ECMO, have achieved treatment success by Day 15. Patients discontinuing prior to Day 15 due to having significantly improved will be considered having achieved treatment success. Patients who died by Day 15, have not achieved treatment success regardless of IMV/ECMO use by Day 15.

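### Protocol 7.3.8 contains an unconditional success rule for patients discontinuing before Day 15; read literally, it contradicts the protocol's own failure rules and differs from the SAP

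*Protocol*

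**What the plan says.** Protocol 7.3.8 (Handling of missing data) scores the primary endpoint for patients who stop before Day 15 through four rules in sequence:

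1. Ventilated at discontinuation: a patient who stops study treatment (or, on standard of care, leaves the study) and "had IMV or ECMO on their last assessment by the time of study treatment discontinuation, will be considered not having achieved treatment success".
2. Never ventilated: "Patients discontinuing prior to Day 15 without ever having initiated IMV/ECMO, will be considered having achieved treatment success by Day 15".
3. No condition: "Patients discontinuing prior to Day 15 will be considered having achieved treatment success".
4. Death: "Patients who died by Day 15, have not achieved treatment success regardless of IMV/ECMO use by Day 15".

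SAP 8.2.1 (Imputation of efficacy endpoints) has the same four rules, but the third reads "Patients discontinuing prior to Day 15 due to having significantly improved will be considered having achieved treatment success". SAP 8.5.1 (Treatment success) repeats that limited version. It adds that a patient who needed IMV or ECMO earlier, but no longer needs it at Day 15 or at early discontinuation, is a success.

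**The concern.** Rule 3 as printed in the protocol covers every patient in rule 1 and gives the opposite result. It also collides with rule 4 for a patient who discontinues and then dies by Day 15, and it leaves rule 2 with nothing to do. The protocol does not say which rule prevails.

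The SAP's limiting phrase removes the clash with rule 1 in practice, since a patient on a ventilator at the last assessment would hardly be recorded as stopping for significant improvement. The protocol sentence is grammatically complete and shows no sign of redaction, so the two current texts state different rules for the primary endpoint.

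At stake is who counts as a failure in a comparison of 18 against 18. Protocol 7.1 allows a result significant at the 5% level in the Stage 2 analysis to be treated as confirmed efficacy and used, where warranted, to seek approval. The rule that produces the counts should therefore be unambiguous.

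**Working it through.** **The texts side by side**

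| Patient discontinuing before Day 15 | Protocol rules 1, 2, 4 | Protocol rule 3, literal | SAP 8.2.1 / 8.5.1 |
|---|---|---|---|
| On IMV/ECMO at last assessment | Failure | Success | Failure |
| Never on IMV/ECMO, alive at Day 15 | Success | Success | Success |
| Earlier IMV/ECMO, no longer required | Not addressed | Success | Success |
| Died by Day 15 | Failure | Success | Failure |

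The conflict lies in the first and last rows.

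**Inputs.** From Protocol 7.1 and 7.3.6: 18 per arm; Stage 1 taken at exactly 9 per arm (the plan says at least 9); Stage 1 efficacy at one-sided p < 0.025; binding futility at p > 0.690; Stage 2 efficacy at p < 0.159; success rates of 50% and 80%. From Protocol 7.3.3.1.1: Fisher's exact test. The documents give no expected discontinuation rate, so every share below is an assumption.

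**Reproducing the plan's figure.** I enumerated all binomial outcomes for 9 v 9 and then 18 v 18, counting a Stage 1 or a Stage 2 crossing as efficacy. Power at 80% v 50% is 73.6%, matching the stated 74%. At 50% v 50% the probability of declaring efficacy is 11.7%. The plan states 9.7% without giving the null rate; the same enumeration gives 9.5% at 70% v 70%. That difference does not come from this sentence.

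**One patient.** With c successes on standard of care and a on active, the one-sided p-value is the sum over x from a to 18 of C(18,x)·C(18,a+c−x)/C(36,a+c). Take c = 9 (assumed).

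- a = 12: 1,391,396,688 / 5,567,902,560 = 0.250, not significant at Stage 2.
- a = 13, after one ventilated discontinuer is rescored: 579,441,600 / 3,796,297,200 = 0.153, below 0.159. SAP Table 1 lists 13 v 9 as an efficacy outcome.
- The same single step from 14/18 to 15/18 moves p from 0.082 to 0.0375.

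**A share of patients.** If a share q of failures is rescored as success, the success rate p becomes p + q(1 − p). For q = 10%, 20%, 30%, a rate of 50% becomes 55%, 60%, 65%, and 80% becomes 82%, 84%, 86%. Running these through the two-stage design:

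| | q = 0 | 10% | 20% | 30% |
|---|---|---|---|---|
| Power (80% v 50%), both arms rescored equally | 73.6% | 67.2% | 60.1% | 52.4% |
| False positive (50% v 50%), both arms equally | 11.7% | 11.6% | 11.1% | 10.4% |
| False positive (50% v 50%), active arm only | 11.7% | 18.6% | 27.5% | 38.1% |

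The last row is an upper limit for each q, because it treats every failure as a surviving patient open to rescoring. If 25% of failures were deaths, which stay failures under rule 4 (assumed), the effective share is 0.75q and the row becomes 16.7%, 22.8%, 30.0%. At 50% deaths it becomes 14.9%, 18.6%, 22.8%.

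**The case against.** The best defence is that the paragraph can be read coherently. If specific rules prevail over the general one, rule 1 settles those ventilated at discontinuation, rule 2 the never ventilated and rule 4 the deaths. Rule 3 then decides only patients who had been ventilated and no longer were. SAP 8.5.1 also scores that group as successes, so on this reading the documents agree. The SAP is the detailed derivation, states the limited version twice, and under SAP 5.2 is to be locked before the Stage 1 analysis. A statistician would very probably follow it, and the protocol sentence looks like one that lost its qualifier.

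Much of this stands. It makes misapplication unlikely, but it relies on a precedence that the protocol does not state.

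Three stronger readings are tempting and are not supported:

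- *That the protocol scores every discontinuer as a success.* The same paragraph expressly fails those ventilated at the last assessment and those who die by Day 15. The defect is a contradiction, not a blanket rule.
- *That the SAP allows success only for significant improvement.* It also gives success to never-ventilated discontinuers and to those no longer needing IMV or ECMO.
- *That the sentence mainly favours the active arms, because study drug would be stopped at intubation.* No section says so. Protocol 5.3.3.1 ties treatment withdrawal to medical necessity in the investigator's opinion or to the patient's wish. Protocol 5.4.7.2 provides for study withdrawal in any arm when a prohibited immunomodulator is started, for example as rescue for worsening. Rule 1 does define discontinuation differently by arm, so imbalance is possible, but its direction and size are not established.

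**Conclusion.** The point holds as an internal contradiction in the protocol, and a mismatch with the SAP, over how the primary endpoint is scored for a patient on IMV or ECMO at discontinuation. It is wrong as written rather than a matter of missing detail, because a stated endpoint rule gives two answers for the same patient.

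On assumed counts, one rescored patient is enough to cross the Stage 2 bound. If the literal sentence were applied equally in both arms to 10–30% of failures, the cost would be power, about 6 to 21 percentage points (73.6 − 67.2 = 6.4; 73.6 − 52.4 = 21.2), with no rise in the false-positive rate. An increase to as much as 18.6%, 27.5% or 38.1% requires rescoring in the active arm alone and no deaths among the failures; it is a bound, not an expectation. All of these shares are assumptions. If the SAP is followed, the design figures do not change.

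**What to change.** Before the Stage 1 analysis, replace the unconditional sentence in Protocol 7.3.8 with the SAP 8.2.1 wording, or delete it. Add one clause to the protocol, mirrored in SAP 8.2.1 and 8.5.1, stating that IMV or ECMO at the last assessment and death by Day 15 take precedence over any success rule for discontinuers. Both failure rules already exist; only their precedence is new. If the sentence is deleted, carry over SAP 8.5.1's rule for patients no longer needing IMV or ECMO at discontinuation, so that the protocol still covers that group.

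The cost is a sentence or two in the next protocol amendment and a matching line in the SAP. Data collection, sample size and stopping bounds are unaffected. Because the trial is open-label, the wording should be settled before the Stage 1 results are seen.
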